9.5.2 Evaluating and Recording of Adverse Events

At each visit all adverse events that are observed, elicited by the Investigator, or reported by the subject, will be recorded in the appropriate section of the AE CRF and evaluated by the Investigator.

Minimum information required for each AE includes type of event, duration (start and end dates), severity, seriousness, causality to study drug, action taken, and outcome.

Severity of AEs will be graded by the Investigator using the following criteria as guidelines:

1. Mild: Nuisance, barely noticeable.
2. Moderate: Uncomfortable, troublesome symptoms not significantly interfering with daily activities or sleep.
3. Severe: Symptoms significantly interfere with daily activities or sleep.

The relationship of the AE to the study drug should be specified by the Investigator, using the following definitions:

1. Not Related: Concomitant illness, accident or event with no reasonable association with study drug.
2. Unlikely Related: The event has little or no temporal sequence from administration of the study drug, and/or a more likely alternative etiology exists.
3. Possibly Related: The event follows a reasonable temporal sequence from administration of study drug **but which could also be explained** by concurrent disease or other factors or medications.
4. Probably Related: The event follows a reasonable temporal sequence from administration of study drug, **but is unlikely to be attributed** to concurrent disease or other factors or medications. A clinically reasonable response may be observed if the study drug is withdrawn or dose reduced.
5. Definitely Related: the event follows a reasonable temporal sequence from administration of study drug and is definitive pharmacologically; cannot be attributed to concurrent disease or other factors or medications. A clinically reasonable response

should be observed if the study drug is withdrawn or dose reduced.

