7.1 ADVERSE EVENTS

Adverse events (AEs) will be coded by System Organ Class (SOC) and Preferred Term (PT) using the Medical Dictionary for Regulatory Activities (MedDRA®, version 16.0/AECODE). The verbatim term will be included in the AE listings.

A treatment-emergent adverse event (TEAE) is defined as an AE that occur or worsen on or after the first dose of study drug in Study 1042-0604 and before the end of the study (including the safety follow-up period). Only TEAEs will be included in summary tables. All AEs, treatment emergent or otherwise, will be presented in subject data listings.

The TEAEs will be summarized as the number (percentage) of subjects with TEAEs within SOC and PT. Subjects who report the same PT on multiple occasions will be counted once for the PT: under the highest severity (severe > moderate > mild) when summarized by severity and under the closest relationship (related > probably related > possibly related > unlikely related > Not related) to study drug when summarized by relationship. If a subject reports multiple PT for a SOC, the subject will be counted only once for that SOC. Treatment related AEs are defined as those events recorded on the CRF as 'Related', 'Probably Related' or 'Possibly Related', others will not be related AEs.

TEAEs will be summarized as below.

- An overview table, including number of subjects with
 - TEAEs
 - serious AEs (SAEs)
 - study drug related TEAEs
 - TEAEs by severity

- TEAEs leading to study discontinuation
- TEAEs leading to death
- TEAE by SOC and PT
- TEAE by SOC, PT, and Severity
- TEAE by PT
- TEAEs by SOC, PT, and Relationship to Study Drug

All AE tables will be sorted by SOC and PT in decreasing frequency of the number and percentage of subjects.

Missing date will be imputed followed table describes how missing date information will be handled:

Partial Missing Start or Stop Date	Imputed Start Date	Imputed Stop Date
Missing month and day, and the year is present	January 1 of that year or first dose date if the year is the same as the year of first dose date	December 31 of that year
Missing day, but year and month are present	First day of that month or first dose date if the year and month are the same as the year and month of first dose date	Last day of that month
Missing month, but year and day are present	Missing month imputed as January	Missing month imputed as December

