7.1.1 Deaths, Serious and Other Significant Adverse Events

The listings of serious AEs, AE leading to study discontinuation, and subjects who died during the study will be provided.

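### SAP 7.1 imputes an adverse event start date missing only its month to January with no first-dose check, so a true on-treatment event can drop out of the TEAE tables

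*SAP*

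**What the plan says.** SAP 7.1 defines a TEAE as "an AE that occur or worsen on or after the first dose of study drug in Study 1042-0604", up to the end of the study including safety follow-up. It then states: "Only TEAEs will be included in summary tables". The same section ends with a table for partial dates. Its start-date column has three rows:

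- **Row 1, month and day missing:** "January 1 of that year or first dose date if the year is the same as the year of first dose date".
- **Row 2, day missing:** the first of the month, or the "first dose date if the year and month are the same as the year and month of first dose date".
- **Row 3, month missing, day and year known:** "Missing month imputed as January". Nothing further is said.

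SAP 2.5 rules out imputation unless otherwise specified, and this table is such a specification. No other section adds a first-dose check for row 3 or treats an event of uncertain date as treatment-emergent by default. SAP 5.2 uses the same table for medications.

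**The concern.** Rows 1 and 2 protect against one particular error: giving an event an artificial start before first dose when the recorded part of the date is compatible with onset on treatment. Row 3 lacks that protection. January is the earliest month of the year, so for most first-dose dates the imputed start falls before first dose wherever the true onset lay. The rule then classifies a true on-treatment event as not treatment-emergent by onset.

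The result is also perverse. If the site had recorded the year alone, row 1 would have kept the event. A record that contains more information is handled less conservatively.

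At stake are the TEAE overview and the tables by system organ class, preferred term, severity and relationship. These are a main output for the primary objective of safety and tolerability, and the error understates them.

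**Working it through.** The plan gives no figure for this point, so there is none to reproduce. The check applies the three rules as written.

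**One worked case (dates assumed).** First dose in Study 1042-0604 is 10 June 2015 and true onset is 20 September 2015.

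| What is missing | Imputed start | On or after first dose? |
|---|---|---|
| Month and day (row 1) | 10 June 2015 | Yes, TEAE |
| Day only (row 2) | 1 September 2015 | Yes, TEAE |
| Month only (row 3) | 20 January 2015 | No, not a TEAE by onset |

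**All dates in one year.** Take every first-dose date *f* in a 365-day year and every true onset from *f* to 31 December. The number of pairs is 365 × 366 / 2 = 66,795. An event is lost when its imputed start is earlier than *f*. For row 3 the imputed start is the recorded day in January, so:

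- **First dose 1 February or later:** every January date precedes *f*, and the loss is 100%.
- **First dose on day *k* of January:** the event is lost when its recorded day of the month is below *k*.
  - 1 January: 0%.
  - 15 January: 154 of 351 onsets, 43.9%.
  - 31 January: 328 of 335 onsets, 97.9%.
  - Mean over the 31 January dates: 47.9%.
- **Average over first-dose dates:** (31 × 0.479 + 334 × 1.000) / 365 = 95.6%.
- **Pooled over date pairs:** 61,057 / 66,795 = 91.4%. This is the same enumeration with more weight on early first-dose dates, which have more onset days left in the year.
- **Rows 1 and 2:** 0 of 66,795.

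**Onsets in a later calendar year.** The imputed January date is then after first dose. With 17, 52 or 106 weeks of follow-up, none is dated before first dose.

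**Share of all on-treatment onsets.** Keep the condition that only the month is missing, but let onset be uniform over follow-up and first dose uniform over the year. The share dated before first dose is then about 80% with 17 weeks of follow-up, 46% with 52 weeks and 23% with 106 weeks.

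**Row 3 with the change proposed below.** The loss is 0 of 66,795.

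**The case against.** The strongest reply is that the pattern hardly occurs. It needs a known day and year with an unknown month. Protocol 9.5.2 requires for each AE its "duration (start and end dates), severity, seriousness, causality to study drug, action taken, and outcome". Events are reviewed at visits about 17 weeks apart, which helps to bound the month, and Protocol 8.6 has data discrepancies resolved with the investigator. Nor is a lost event hidden: "All AEs, treatment emergent or otherwise, will be presented in subject data listings", and "The listings of serious AEs, AE leading to study discontinuation, and subjects who died during the study will be provided". The study has one arm, is descriptive, and by SAP 9 ended early with few patients. All of this stands, and it holds the point to minor. It does not make the rule right. The SAP chose to provide for this pattern, listings do not correct the tables, and with few patients a single event can show in a preferred-term row.

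A second reply is that SAP 7.1 never says in words that the imputed date sets the TEAE flag, whereas SAP 5.2 does state what its table is for. That is true, and the link is an inference. But the table sits in the section that defines TEAEs, no other use is given, and the first-dose clauses in rows 1 and 2 serve only to place events relative to first dose.

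A third reply is that rows 1 and 2 never contradict a recorded part of the date, while moving a row 3 date to first dose usually overwrites the recorded day: in 59,078 of the 61,057 pairs moved (96.8%). That is correct for the date itself. It has no bearing on whether the event counts as a TEAE.

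Finally, the 95.6% figure is easily over-read. It is conditional on the pattern and on onset in the first-dose year. It is not a share of on-treatment AEs in general.

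**Conclusion.** The concern holds and is minor. Followed as written, row 3 dates a true on-treatment AE in the first-dose year before first dose in every case when first dose is 1 February or later, and in 0% to 98% of cases when it is in January. The average over first-dose dates is 95.6%. Rows 1 and 2 lose none.

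These figures rest on four conditions: exactly the month is missing; first-dose and onset dates are uniform; the imputed start determines the TEAE flag; and no worsening after first dose is recorded that would qualify the event on its own. Events starting in a later calendar year are unaffected. The documents give no count of such dates, so no effect on any TEAE total can be stated, and it may be nil. The direction is clear, however: the rule can only take true on-treatment events out of the safety tables.

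**What to change.** In the SAP 7.1 partial-date table, add one clause to the start-date cell of row 3: if the year equals the year of first dose and the January date falls before first dose, impute the first dose date, unless the stop date shows that the event ended before first dose. Otherwise keep the January date. A January date already on or after first dose is left alone.

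The cost is one clause and no new data. The price is that a truly pre-dose event in the first-dose year, with no informative stop date, would be counted as a TEAE. That is the conservative direction and is what row 1 already does. Few such events should arise, because Protocol 8.5.1.3.1 sends events from Study 1042-0603 that are unresolved at entry, or judged significant, to medical history. If the recorded day should stay visible, the listing can show the date as collected beside the imputed one.

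The identical row in SAP 5.2 could be aligned for consistency. Its effect there is small: at most it would normally add a prior label to an on-treatment medication, because the December stop imputation normally keeps the drug concomitant.

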7.1.1 Deaths, Serious and Other Significant Adverse Events

The listings of serious AEs, AE leading to study discontinuation, and subjects who died during the study will be provided.

7.2 CLINICAL LABORATORY PARAMETERS

Laboratory assessments include hematology, clinical chemistry, and urinalysis as in Table 2:

Table 2: Clinical laboratory parameters:

Clinical Chemistry	Hematology	Urinalysis
Total Bilirubin	Hemoglobin	pH
AST (SGOT)	Hematocrit	Color
ALT (SGPT)	Erythrocytes	Transparency

BUN	Leukocytes + differential	Specific Gravity
Glucose	Thrombocytes (platelet count)	Urobilinogen
Potassium		Ketones
Sodium		Protein
Calcium		Glucose
Alkaline Phosphatase		Hemoglobin
Chloride		
Creatinine		
CO ₂		
Total Protein		
Serum Albumin		

ALT = alanine transferase; AST = aspartate transferase; BUN = blood urea nitrogen

All laboratory parameters will be presented in Système International (SI) units. Quantitative results (including actual value, and change from baseline) for hematology and chemistry will be summarized using descriptive statistics by visit. The number (and percentage) of subjects with urine abnormalities will be summarized by visit.

All laboratory data will be included in the listings. A pregnancy listing will be provided separately.

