In Study 1042-0600 and in the ganaxolone development program overall, no clinically significant trends in changes from baseline electrocardiogram (ECG) recordings, vital signs, or physical or neurological examinations have been noted in the clinical studies, and no mean changes from baseline in clinical labs have been identified. Transient increases in LFTs ($>3\times\text{ULN}$) have been noted in less than 1% of subjects treated with ganaxolone. Serious adverse events (SAEs) reported in the ganaxolone epilepsy trials were considered by a Scientific Advisory Board to be usual for the population without any pattern attributable to ganaxolone. Profiles of the most frequently reported AEs have been consistent with the predicted pharmacology of the drug.

Due to the favorable tolerability profile of ganaxolone in Study 1042-0600 and its open-label extension, the current study is designed to further examine the safety, tolerability and efficacy in a second year of open-label treatment with ganaxolone when used as an add-on therapy in adult subjects with drug-resistant partial-onset (focal) seizures.

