8.7.1.4 Analysis of Safety Variables

Adverse events (AEs) will be tabulated by overall, system organ class (SOC), and Preferred Term using the MedDRA v.16.0 coding system. Incidence and percentage of adverse events, by dose and overall. Additional tables, with AEs subset by severity and by relationship to drug as assessed by the investigator will be presented. Subset listings will be produced for adverse events that cause withdrawal and for SAEs.

Laboratory data, vital signs and ECGs will be summarized using descriptive statistics. Important changes in laboratory, ECG values and vital signs will be flagged in data listings. Listings of most abnormal changes will be provided.

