7.3 VITAL SIGNS, 12-LEAD ECG, PHYSICAL AND NEUROLOGICAL EXAMINATIONS, AND C-SSRS

7.3.1 Vital Signs

Vital signs include temperature, blood pressure, pulse rate, respiration rate, height, weight and BMI.

All vital signs will be presented in Système International (SI) units. Quantitative results (including actual value, and change from baseline to each post-baseline visit) will be summarized using descriptive statistics by post-baseline time point for each parameter.

Listings of vital signs with abnormal flags will be provided.

7.3.2 12-Lead ECG

12-lead ECG data will be reported in listing.

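### The SAP does not carry over the protocol's laboratory and ECG flags or its listing of most abnormal changes, and no planned output counts subjects who reached the study's own liver or QTc limits

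*SAP*

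**What the plan says.** Protocol 8.7.1.4 makes three commitments on these data. The first is a summary: "Laboratory data, vital signs and ECGs will be summarized using descriptive statistics". The second concerns how extreme values are marked: "Important changes in laboratory, ECG values and vital signs will be flagged in data listings". The third is a separate display of the extremes: "Listings of most abnormal changes will be provided".

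SAP 7.2 plans this for haematology and chemistry: "Quantitative results (including actual value, and change from baseline) for hematology and chemistry will be summarized using descriptive statistics by visit". For urinalysis it plans a count: "The number (and percentage) of subjects with urine abnormalities will be summarized by visit". It closes with "All laboratory data will be included in the listings", without mentioning flags. SAP 7.3.1 does provide abnormal flags in the vital-signs listings. SAP 7.3.2 says "12-lead ECG data will be reported in listing", again with no flags. No listing of most abnormal changes appears anywhere in the SAP.

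Three other provisions bear on the point:

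- SAP 2.1 defines the continuous summary as n, mean, SD, median, minimum and maximum, and allows a summary table to be left out when data are sparse.
- SAP 2.3 keeps unscheduled results out of the tables and reports them only in listings.
- SAP Section 9 lists changes from the protocol. It declares that ECG is listing-only, because of early termination and low patient numbers. It does not mention laboratory or ECG flags or the most-abnormal listing.

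**The concern.** Safety and tolerability are the primary objective. Protocol 8.3.4.1 sets numerical limits for this study: absolute QTc and QT values and a QTc increase from Visit 1 (item 1), and multiples of ULN for ALT/AST, alone or with bilirubin, duration or symptoms (item 11). A reader of the final report will want to know how many subjects reached each of them. The SAP provides no such number. It also leaves out the two devices by which the protocol meant to draw attention to extreme values.

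The protocol's own background shows why this matters. Its Introduction says that "no mean changes from baseline in clinical labs have been identified", and also that transient liver-test rises above 3×ULN occurred in under 1% of treated subjects. A finding of that kind appears in a few individuals and need not appear in group averages.

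**Working it through.** **Step 1: compare the texts.** The plan gives no figure to reproduce. Sample size is whoever is eligible from Study 1042-0603.

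| Item | Protocol 8.7.1.4 | SAP | Declared in SAP Section 9? |
|---|---|---|---|
| Laboratory flags | Yes | Not mentioned (7.2) | No |
| ECG flags | Yes | Not mentioned (7.3.2) | No |
| Vital-sign flags | Yes | Yes (7.3.1) | Not needed |
| Listing of most abnormal changes | Yes | Not mentioned | No |
| ECG descriptive summary | Yes | Listing only | Yes |
| Count of subjects over liver or QTc limits | Not promised | None | Not needed |

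Because the SAP writes flags in for vital signs, flags for laboratory and ECG data cannot safely be taken as implied.

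**Step 2: ask whether the planned statistics give the count.** The values here are assumed: 50 subjects at one visit, everyone else at 0.5×ULN.

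- Visit A, one subject at 8.1×ULN: mean = (49×0.5 + 8.1)/50 = 0.652; median 0.5; minimum 0.5; maximum 8.1; subjects above 3×ULN = 1.
- Visit B, two at 3.1 and one at 8.1×ULN: mean = (47×0.5 + 2×3.1 + 8.1)/50 = 0.756; median 0.5; minimum 0.5; maximum 8.1; subjects above 3×ULN = 3.

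The means differ, but a count cannot be read from them. The maximum gives one value per visit, in SI units and not as a multiple of ULN. By-visit summaries of single analytes also cannot show the joint ALT/AST and bilirubin criterion or the more-than-2-weeks criterion.

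**Step 3: see how far one extreme value moves the mean.** Shift = (extreme − 0.5)/n. SE = 0.2/√n, with an assumed SD of 0.2×ULN among the others. All values are in ×ULN.

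| n (assumed) | Shift, one at 3.1 | Shift, one at 8.1 | SE |
|---|---|---|---|
| 20 | 2.6/20 = 0.13 | 7.6/20 = 0.38 | 0.045 |
| 50 | 2.6/50 = 0.052 | 7.6/50 = 0.152 | 0.028 |
| 100 | 2.6/100 = 0.026 | 7.6/100 = 0.076 | 0.020 |
| 350 (protocol maximum) | 2.6/350 = 0.007 | 7.6/350 = 0.022 | 0.011 |

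At small n the shift is not hidden: 0.152/0.028 is over 5 standard errors. The printed SD would rise too. At n = 50 with one value of 8.1, SD = √[(48×0.2² + (49/50)×7.6²)/49] = 1.09; with one value of 3.1, replacing 7.6 by 2.6 gives 0.42. The table would therefore signal that something extreme happened, but not in how many subjects.

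**Step 4: ask how likely a case is.** The protocol says only under 1% above 3×ULN; 0.5% and 1% are assumed here. P(at least one) = 1 − (1 − p)^n.

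| n | p = 0.5% | p = 1% |
|---|---|---|
| 20 | 9.5% | 18.2% |
| 50 | 22.2% | 39.5% |
| 100 | 39.4% | 63.4% |
| 350 | 82.7% | 97.0% |

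**Step 5: check the other routes to a count.** Protocol 9.5.1 and 9.5.2 make a laboratory value an adverse event when the investigator judges it clinically significant or it requires intervention. Protocol 8.3.4.1 lets subjects above 3× and up to 8×ULN without signs or symptoms continue at the investigator's discretion, so discontinuation outputs can miss them. Confirmatory liver tests may fall at unscheduled visits, which the tables exclude. The QTc increase runs from Visit 1, whose ECG is held in the 1042-0603 database (schedule footnote 3), while the SAP safety baseline is the last value before first treatment in that study. The ECG listing may therefore lack the reference value needed to find a crossing by hand.

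**The case against.** The strongest reply is that nothing is lost. A reader might infer that the SAP only averages chemistry results. It does not: SAP 2.1 prints SD, minimum and maximum, and SAP 7.2 lists every value. An extreme scheduled result is therefore visible, and in a small study a full listing can be read subject by subject. That stands.

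A reader might also infer that the SAP cancelled the flags. It is silent on them, which is weaker than removal, although Section 9 is where a removal should be declared. Nor did the SAP break a promise to count limit crossings, since protocol 8.7.1.4 promised flags and listings only. The count table is an improvement, judged against the study's own limits.

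It would also be too strong to say that no output could register such subjects. Adverse-event tables, the listing of events leading to discontinuation, and disposition reasons may do so. They are not specific to a threshold, and they depend on what the investigator recorded.

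Early termination and low numbers are a fair reason to drop an ECG summary table. They do not explain leaving flags out of a listing that will be produced anyway. Low numbers do mean that a count table may be mostly zeros: at a rate under 1%, fewer than 50×0.01 = 0.5 subjects above 3×ULN are expected among 50.

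**Conclusion.** The point holds as an undeclared mismatch between protocol and SAP, together with a reporting gap in the primary safety analysis. Laboratory flags, ECG flags and the most-abnormal listing are committed to in protocol 8.7.1.4, absent from the SAP, and not covered by Section 9. Separately, no planned output states how many subjects reached the liver or QTc limits in protocol 8.3.4.1.

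The consequence is moderate. The data are listed and the worst scheduled value at each visit is shown, so the loss is of emphasis and of a count, not of information. This conclusion rests on the text comparison. The numerical examples only illustrate it, at assumed n, SD and event rates, because the documents do not give the number of subjects enrolled. They should not be read as showing that the planned tables would conceal an extreme value.

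**What to change.** 1. In SAP 7.2 and 7.3.2, restore the laboratory and ECG flags and the listing of most abnormal changes. For ALT/AST, bilirubin and QTc, use the limits already written in protocol 8.3.4.1 items 1 and 11. Otherwise, declare the removal, with a reason, in SAP Section 9.
2. As an improvement beyond the protocol's commitment, add one table of n (%) of assessed Safety Population subjects who, at any time after the first 1042-0604 dose and with unscheduled results included, had:
   - ALT or AST above 3×, 5× or 8×ULN;
   - ALT or AST above 3×ULN with total bilirubin above 2×ULN;
   - a QTc or QT value above the absolute limits of item 1.
3. Show the criteria that need linkage in the flagged listing and not in the table: ALT/AST above 5×ULN for more than 2 weeks, ALT/AST above 3×ULN with symptoms, and a QTc increase above 60 msec from Visit 1. Take the Visit 1 ECG from the 1042-0603 database.

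The cost is SAP wording, listing flags, one derived table and a link to the Visit 1 ECG. No new data collection and no new clinical limit is involved. The downside is a little extra programming for a table that may be mostly zeros at low numbers.
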